2.2 Purpose and Rationale for Study

This trial is looking at patient satisfaction and cost comparison between inpatient and outpatient preinduction cervical ripening. The method will be compared with inpatient pre-induction cervical ripening and patients admitted to the hospital in labor. Time from initiation of method, time in labor and delivery and time from onset of labor to delivery, and rate of achieving a vaginal delivery within 24 hours will be evaluated.

This protocol outlines a randomized trial of 200 women evaluating placement of Cervidil to the posterior vaginal fornix to soften the cervix in preparation for induction of labor. 100 patients will be randomized into the inpatient cervical ripening arm, and 100 to the outpatient cervical ripening arm. The study will not be powered for fetal or newborn mortality.

Increasing patient comfort, patient satisfaction, and inpatient costs will benefit future patients and healthcare for women who require/desire induction of labor.

2.3 Product being investigated:

Cervidil (outpatient cervical ripening) – Cervidil

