3.1 Primary Objectives

To show that when compared to patients admitted to the hospital for cervical ripening:

- a. From the time of admission, patients in the outpatient cervical ripening arm will progress to the second stage of labor in less time.
- b. Patients in the outpatient cervical ripening arm will have more overall satisfaction.
- c. The total overall cost of care for the encounter will be reduced for the group in the outpatient cervical ripening arm.
- d. Patients in the outpatient cervical ripening arm will spend less total time in the hospital.
- e. Cesarean section rates will be similar.

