3.3.2 Secondary endpoints

- Time of delivery
 - Vaginal Delivery
 - Assisted Vaginal Delivery
 - o Cesarean Delivery

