4.4.2 Maternal Secondary Outcomes

- Patient satisfaction as measured by patient satisfaction/pain/anxiety surveys.
- Vaginal delivery rate
- Operative Vaginal delivery rate.
- Cesarean delivery rate.
- Start of oxytocin until delivery
- Time of delivery until discharge
- Time of admission until discharge

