5.1 Data Relevant to the Primary Outcome

5.1.1 Sample Size and Power

- 1. 200 women randomized to two groups for comparison will be enrolled in the study to participate in the research group (receiving Cervidil insert). Data will be collected on the comparison group (all patients admitted cervical ripening and induction of labor) during the same time period.
- 2. With 200 patients in each group a standard two sample t test has 95% power to detect a difference of 0.36 times the standard deviation and 80% power to detect differences of 0.28 times the standard deviation. For example, if the mean time from admitting to delivery is 10 hours with a standard deviation of 2 hours (meaning that most (95%) times are in the range from 6 to 14 hours) then with this sample size we would have 95% power to detect a reduction of 43.2 minutes in the treatment group and a 80% power to detect a difference of 33.6 minutes. These numbers will differ if the true standard deviation is different from 2 hours.

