5.3 Analysis Plan

Primary analysis will be done using 2 sample t-tests on the numeric outcomes with the possibility of using the log of the outcome when the outcome is skewed (as is common for waiting times and cost variables). If the data is not sufficiently normal after logging, then a 2 sample permutation test on the means will be used instead. For categorical outcomes (e.g. delivery type) a chi-squared test will be used to compare the proportion in each category between the treatment and control groups. All tests will be performed at a 5% significance level. The p-values will be reported both unadjusted for multiple outcomes and also adjusted using the False Discovery Rate method. Conclusions will be made using the unadjusted values since each outcome is of interest by itself and they are predetermined.

Additional exploratory data analysis will be done using linear model including regression and logistic regression to adjust for other variables of interest. Any interesting results will be reported as exploratory with need for confirmation since the potential results are not on a predetermined list.

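### Objective 3.1e sets out to show that cesarean rates are similar, but the plan offers only a test of difference and no criterion for similarity

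*Combined protocol and SAP*

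**What the plan says.** Section 3.1 (Primary Objectives) opens "To show that when compared to patients admitted to the hospital for cervical ripening" and lists as item e: "Cesarean section rates will be similar". No margin, direction or reference rate is attached.

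Section 5.3 (Analysis Plan) covers delivery type as follows: "For categorical outcomes (e.g. delivery type) a chi-squared test will be used to compare the proportion in each category". All tests are at the 5% level, and "Conclusions will be made using the unadjusted values since each outcome is of interest by itself and they are predetermined". Logistic regression is mentioned only as exploratory work that needs confirmation.

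Elsewhere the outcome is not primary. Section 3.3.2 lists "Cesarean Delivery" under secondary endpoints, and section 4.4.2 lists "Cesarean delivery rate" under maternal secondary outcomes. It is absent from the study hypotheses (1.2), the primary endpoints (3.3.1) and the primary outcomes (4.4.1).

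On size, section 2.2 says "100 patients will be randomized into the inpatient cervical ripening arm, and 100 to the outpatient cervical ripening arm". Section 5.1.1 instead reasons from 200 per group ("With 200 patients in each group a standard two sample t test has 95% power"), and only for a continuous time outcome. The documents contain no expected cesarean rate and no power or precision statement for it.

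**The concern.** The null hypothesis of a chi-squared test is that the proportions are equal. Rejecting it supports a difference; failing to reject it says only that the data did not rule out equality. The data may equally fail to rule out a sizeable excess of cesareans. A claim of similarity needs either an interval judged against a stated margin, or an estimate reported with its precision and no claim attached. Section 5.3 has neither, yet it promises conclusions drawn from p-values.

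What is at stake is the reassurance that accompanies the time and cost objectives. Section 2.1 frames the aim as lowering cost while keeping outcomes at least as good. If outpatient ripening saves time and money, readers will ask whether it does so without more cesareans, and 3.1e is the objective that should answer. As written, the only result available to support it is a non-significant p-value, which at this sample size is weak evidence.

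**Working it through.** **The plan's own power figure.** Section 5.1.1 gives 95% power at 0.36 SD and 80% at 0.28 SD with 200 per group. For a two-sided 5% test, power ≈ Φ(d·√(n/2) − 1.96).

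- d = 0.36: Φ(3.60 − 1.96) = Φ(1.64) = 0.950
- d = 0.28: Φ(2.80 − 1.96) = Φ(0.84) = 0.800

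Both figures reproduce. They imply two-sided testing, which 5.3 does not state, and they say nothing about cesarean delivery.

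**Inputs for cesarean delivery**

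- Women per arm, n: 100 (section 2.2), with 200 (section 5.1.1) as the alternative.
- Test: uncorrected 2×2 chi-squared, cesarean versus not, two-sided 5%. Section 5.3 could also mean one test across the three delivery types; the 2×2 form is my assumption.
- Inpatient cesarean rate, p: not in the documents; assumed 10% to 30%.
- True increase: 10 percentage points, my illustration. The documents neither give nor imply a figure.

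**Step 1. Chance of a significant result when the true increase is 10 points.** I enumerated all pairs of binomial counts and summed the probability of those with p < 0.05.

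| Inpatient rate | Power, n = 100 | Power, n = 200 |
|---|---|---|
| 10% | 0.518 | 0.811 |
| 15% | 0.431 | 0.713 |
| 20% | 0.371 | 0.639 |
| 25% | 0.342 | 0.590 |
| 30% | 0.316 | 0.558 |

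The complement is the chance that such an increase goes undetected: 48% to 68% at 100 per arm and 19% to 44% at 200. With a continuity correction, power at 100 per arm falls further, to 0.425 down to 0.263.

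**Step 2. Precision.** When both true rates equal p, the 95% half-width is 1.96·√(2p(1−p)/n).

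- n = 100: p = 10% gives 1.96·√(0.18/100) = 0.083; p = 30% gives 1.96·√(0.42/100) = 0.127
- n = 200: 0.059 and 0.090

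**Step 3. A concrete result.** Take 20/100 inpatient and 32/100 outpatient. The pooled rate is 0.26.

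- χ² = 0.12² / (0.26 × 0.74 × 2/100) = 3.74, p = 0.053: not significant
- SE = √(0.20×0.80/100 + 0.32×0.68/100) = 0.0614
- 95% CI = 0.12 ± 1.96 × 0.0614, or about 0 to 24 points

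Against 20/100, the first significant excess is 33/100 (p = 0.037).

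**Step 4. Could a margin be met at this size?** For illustration, take a 10-point margin judged against the upper 95% limit, with equal true rates. The chance of success is Φ(0.10/√(2p(1−p)/n) − 1.96).

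- n = 100: 0.654, 0.508, 0.424, 0.372, 0.338 for p = 10, 15, 20, 25, 30%
- n = 200: 0.915, 0.800, 0.705, 0.637, 0.588

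For 80% power, n per arm = (1.96 + 0.8416)²·2p(1−p)/0.10², which gives 142, 201, 252, 295 and 330.

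**The case against.** The best defence is that 3.1e was never meant as a confirmatory claim. The study hypotheses in 1.2 cover time, cost and satisfaction only, and every endpoint or outcome list either treats cesarean delivery as secondary or omits it. On that reading, item e is a loosely worded reassurance placed under a lead-in that suits items a to d. This may well be the history, and it argues against ranking the point higher. It does not remove the contradiction: section 3.1 is headed Primary Objectives and sets out to show similarity, and a secondary claim of similarity would need a criterion too. If only description was meant, rewording the objective is the right remedy.

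A second defence is that the plan nowhere says a non-significant result will be read as similarity. That is correct. The 48% to 68% above is the chance of a non-significant result; it becomes the chance of a wrong conclusion only if that reading is made. But the plan provides no other way to reach 3.1e.

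Third, the size depends on unresolved design questions. Section 5.1.1 also mentions a comparison group of all patients admitted for ripening and induction, of unstated size. If, purely for illustration, 100 outpatient women were compared with 500 such patients, power for the 10-point increase would be 77% to 50% over the same rates. The extent of the gap would shrink; the missing criterion would remain.

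**Conclusion.** The concern holds. The planned analysis cannot deliver objective 3.1e, because a test of difference has no outcome that establishes similarity and the plan supplies no other rule. This conclusion follows from the text and needs no numerical assumption.

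Its practical weight does rest on assumptions: an inpatient cesarean rate of 10% to 30%, a 2×2 two-sided test, and a 10-point increase chosen for illustration. Under these, non-significance at the randomised 100 per arm is compatible with a substantial excess of cesareans. The problem is smaller but still present at 200 per group. The inconsistent status of the outcome across 3.1, 3.3.2 and 4.4.2 is a secondary defect of the same item. The sponsor should correct this; the minimum correction is mainly one of wording.

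**What to change.** **Minimum change**

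- Reword 3.1e as estimating the difference in cesarean rates, outpatient minus inpatient, and give the outcome one status across 3.1, 3.3.2 and 4.4.2.
- In 5.3, add the risk difference with a two-sided 95% confidence interval, and say whether the chi-squared test is cesarean versus not or spans all delivery types.
- State the expected precision: about ±8 to ±13 points at 100 per arm if the true rates are equal and lie between 10% and 30%.
- State that a non-significant chi-squared test will not be read as similarity.

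The cost is a few sentences and one interval, with no change to enrolment or procedures. The price is a weaker claim.

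**If a not-worse claim is to be kept**, the sponsor must choose and justify a margin before anyone involved in setting it sees outcomes by arm. The six-monthly interim analyses in 5.4 and the committee's look after five participants in 7.2 make early action sensible. The claim would then be judged by the upper 95% limit against that margin. This route is costlier: at an illustrative 10-point margin, 100 per arm gives only a 34% to 65% chance of success when the true rates are equal, and 80% power needs about 142 to 330 women per arm. It is optional; the minimum change is enough to resolve the point.

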6.1 Data Collection Forms

The data collection forms will include a 24 item study specific survey consisting of questions from the previously validated DoD/VA pain Supplemental Questions scale, study specific questions, and a 32 item survey to be completed by all patients seen at Intermountain.

- DoD/VA Pain Supplemental Questions (Cleeland & Ryan, 1994)
- HCAHPS (HCAHPS Fact Sheet. June, 2015, http://www.hcahpsonline.org/Facts.aspx)

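### Section 5.3 has no route for ordered survey responses; if a multi-level satisfaction item is treated as categorical, the chi-squared test is a poor match for objective 3.1b

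*Combined protocol and SAP*

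**What the plan says.** - **Objective.** Section 3.1 (Primary Objectives), item b: "Patients in the outpatient cervical ripening arm will have more overall satisfaction". The claim has a direction. Section 1.2 states the same hypothesis.
- **Outcome.** Section 4.4.2 lists satisfaction as a maternal secondary outcome: "Patient satisfaction as measured by patient satisfaction/pain/anxiety surveys". It gives no item, total score, response scale or cut-off.
- **Instruments.** Section 6.1 describes a "24 item study specific survey" and a 32-item survey, and lists HCAHPS. It gives no response categories or scoring rule.
- **Tests.** Section 5.3: "Primary analysis will be done using 2 sample t-tests on the numeric outcomes", possibly on the log scale if skewed, with a permutation test on the means if the logged data are still not normal enough. Then, for categorical outcomes, with delivery type as the only example: "a chi-squared test will be used to compare the proportion in each category between the treatment and control groups". Also: "All tests will be performed at a 5% significance level".
- **Other models.** Linear and logistic regression are exploratory only. No rank, trend or ordinal method is named anywhere.

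Section 5.3 does not mention satisfaction, pain or anxiety.

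**The concern.** Survey answers on satisfaction, pain and anxiety usually run from low to high. With no total score or scoring rule defined, an analyst who keeps an item as response levels would fall under the chi-squared sentence. With K levels, that is an omnibus test on K−1 degrees of freedom. It gives the same result however the levels are shuffled, so it spreads its power over every kind of difference between arms, including differences that are not more satisfaction.

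Two things are at stake. A real upward shift could be missed. A significant p-value could also reflect only more polarised answers and then be read as support for 3.1b. Section 5.3 draws its conclusions from unadjusted p-values on the ground that the outcomes are fixed in advance, yet for satisfaction the choice between numeric and categorical handling is still open.

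**Working it through.** **1. The plan's own power figure.** The plan states no power for satisfaction or for any chi-squared test. Its t-test figures (5.1.1, 200 per group) show which test level is meant. Power = Φ(d·√(n/2) − 1.96).
- d = 0.36: 0.36 × 10 − 1.96 = 1.64, power 94.95% (stated 95%).
- d = 0.28: 0.28 × 10 − 1.96 = 0.84, power 79.96% (stated 80%).

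Both reproduce with a two-sided 5% level, which is used below. The arm size is the 100 per arm of section 2.2. The 200 per group in 5.1.1 conflicts with that, which is a separate matter.

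**2. Inputs that must be assumed.** The documents give no response formats or distributions. Assumed inpatient distributions, lowest to highest level:
- four levels: 5/15/35/45%
- five levels: 5/10/20/35/30%

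The outpatient arm is shifted upward by a common odds ratio: logit P₁(Y ≤ k) = logit P₀(Y ≤ k) − ln OR. For example, with four levels and OR 2.0, the cumulative odds 0.0526, 0.25 and 1.222 are halved, which gives 2.6/8.5/26.8/62.1%.

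**3. Power against an upward shift** (4,000 simulated trials per row, Pearson chi-squared against Wilcoxon rank-sum):

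| Levels | OR | Chi-squared | Wilcoxon | Loss (points) |
|---|---|---|---|---|
| 4 | 1.8 | 42% | 58% | 16 |
| 4 | 2.0 | 54% | 71% | 17 |
| 4 | 2.2 | 66% | 82% | 16 |
| 5 | 1.8 | 39% | 63% | 24 |
| 5 | 2.0 | 54% | 76% | 22 |
| 5 | 2.2 | 67% | 86% | 19 |

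The simulation error of each power is at most √(0.5 × 0.5/4000) = 0.8 points. A repeat run gave losses of about 16 to 23 points.

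**4. Other assumed distributions** (20,000 trials, 100 per arm, chi-squared vs Wilcoxon):
- five levels 10/20/40/20/10%: 20% vs 35% at OR 1.5; 37% vs 59% at 1.75; 55% vs 77% at 2.0
- four levels 5/15/30/50%: 20% vs 31%; 36% vs 52%; 52% vs 70%

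The loss here is 11 to 22 points. With 200 per arm, the five-level case gives 40% vs 61%, 69% vs 87% and 88% vs 97%.

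**5. Significance without a gain.** Take 100 per arm with counts 5/15/35/45 and 15/5/25/55.
- Means, levels scored 1 to 4: (5 + 30 + 105 + 180)/100 = 3.20 and (15 + 10 + 75 + 220)/100 = 3.20.
- Expected counts are 10/10/30/50 in each arm. Chi-squared = 2 × (25/10 + 25/10 + 25/30 + 25/50) = 12.67 on 3 df, p = 0.005.
- Wilcoxon p = 0.43; t-test p = 1.0.

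In repeated sampling where only the spread differs (10/20/40/20/10% vs 20% in each level), chi-squared rejects in 86% of trials, Wilcoxon in 6% and the t-test in 5%. With a milder change (vs 17.5/20/25/20/17.5%), chi-squared rejects in 58% and the other two in about 5%.

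**6. The numeric route.** In the step 2 scenarios at OR 2.0, the t-test on level scores has 68% power vs 71% for Wilcoxon (four levels) and 71% vs 75% (five levels). Over OR 1.8 to 2.2 it trails by about 3 to 4 points. The log does not suit these scores: skewness goes from −0.85 to −1.66 (four levels) and from −0.73 to −1.64 (five levels).

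**The case against.** A reader might infer that the plan sends satisfaction to the chi-squared test. The documents do not say so. The only categorical example in 5.3 is delivery type, which is unordered and correctly tested. Objective 3.1b speaks of overall satisfaction measured by multi-item surveys. A summed or averaged score, or an item coded as numbers, would be numeric and go to the t-test or the permutation test on means. Both use order and show direction. This objection stands, and it makes the point conditional.

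A reader might also infer that a chi-squared analysis could never support the directional claim. That goes too far. A comparison of the top category against the rest has a readable direction and, at OR 2.0, 69% power vs 71% for Wilcoxon with four levels (65% vs 75% with five). Category proportions can also be read beside a multi-category test. The limit is on the multi-category p-value taken alone. The plan, however, sets no top-category rule.

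The log is only a possibility in 5.3, explained by waiting times and costs, and the permutation fallback largely answers the skew problem. It remains only as a minor point.

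Finally, every distribution above is assumed, and nothing in the documents suggests that outpatient ripening polarises answers. The sizes are therefore illustrative. The direction of the power loss was the same in every multi-category shift scenario tried.

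**Conclusion.** The point holds in conditional form. Section 5.3 has no rule for ordered responses and does not say whether satisfaction is numeric or categorical. If a multi-level item is taken as categorical, the stated test loses about 16 to 23 power points at 100 per arm (four or five levels as assumed, proportional shift, odds ratios 1.8 to 2.2). It can also reject when only the spread changes, so its p-value alone is a poor test of 3.1b. If the item or score is taken as numeric without the log, the loss is only about 3 to 4 points and the issue is minor.

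The change is worth making: 3.1b is listed among the primary objectives, even though 4.4.2 ranks satisfaction as secondary. In the multi-level shift scenarios tried, the rank test was at least as powerful as each route that 5.3 offers.

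**What to change.** In section 5.3:

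1. Add that ordered survey responses (satisfaction, pain, anxiety) are compared between arms with the Wilcoxon rank-sum test, and that the effect is reported as a proportional-odds common odds ratio with a 95% CI.
2. Name the one satisfaction item or score that tests objective 3.1b. If a summed score is chosen, use the t-test or the permutation test on means, without the log.
3. Keep the chi-squared test for unordered outcomes such as delivery type.

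The cost is a few sentences in the analysis plan, settled before outcome data are examined. No new data, procedures or participants are needed. The one downside is a routine check of the proportional-odds assumption.

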3.3 Primary and Secondary Endpoints

3.3.1 Primary endpoints

- Time of complete dilation
- Date/time of hospital discharge

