4.4 Study Outcome Measures and Ascertainment

4.4.1 Primary Outcome

- Time of admission for induction (as recorded in iCentra) to complete dilation
- Total hospital costs charged to patient, as obtained by Intermountain Healthcare billing services.

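### Sections 3.1, 3.3.1 and 4.4.1 give three different primary lists, and 5.3 draws conclusions from unadjusted 5% tests without naming the outcome that decides the trial

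*Combined protocol and SAP*

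**What the plan says.** Section 3.1 sets five primary objectives: shorter time from admission to second stage (a), more satisfaction (b), lower cost (c: "The total overall cost of care for the encounter will be reduced for the group in the outpatient cervical ripening arm"), less hospital time (d: "Patients in the outpatient cervical ripening arm will spend less total time in the hospital") and comparable cesarean rates (e: "Cesarean section rates will be similar").

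Section 3.3.1 has two primary endpoints: the time of complete dilation and "Date/time of hospital discharge".

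Section 4.4.1 also has two primary outcomes, but a different pair: "Time of admission for induction (as recorded in iCentra) to complete dilation" and "Total hospital costs charged to patient, as obtained by Intermountain Healthcare billing services".

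Section 4.4.2 lists satisfaction, cesarean rate and "Time of admission until discharge" as secondary. Section 4.4.4 adds cost to the hospital system as an outcome of its own.

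Section 5.3 applies the primary analysis to the numeric outcomes in general, tests all outcomes at 5%, and reports p-values both unadjusted and FDR-adjusted. On which set counts, it says: "Conclusions will be made using the unadjusted values since each outcome is of interest by itself and they are predetermined".

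Section 5.1.1 illustrates power with time from admission to delivery and assumes 200 patients in each group. Section 2.2 randomizes 200 women in total, 100 to each arm.

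**The concern.** Section 5.3 justifies unadjusted conclusions on the ground that the outcomes are predetermined. The outcomes are named in advance, but their rank is not. Satisfaction, cost, hospital stay and cesarean rate are each primary in one place and either secondary or absent in another.

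If one of them is significant and the others are not, the protocol can be cited in support of calling that one primary. A reader could not tell from the text whether that rank was settled before the data were seen. Reporting both sets of p-values makes selection more visible, but it does not say which result decides the trial.

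The sample size does not settle the matter either. Its worked example concerns an outcome on none of the primary lists, at twice the number per arm that 2.2 provides.

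**Working it through.** **1. The lists side by side**

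| Outcome | 3.1 | 3.3.1 | 4.4.1 | Elsewhere |
|---|---|---|---|---|
| Complete dilation | primary (a) | primary | primary | |
| Satisfaction | primary (b) | absent | absent | secondary in 4.4.2 |
| Cost | primary (c), type not stated | absent | primary, patient charges | system cost separate in 4.4.4; 1.1 also separates the two |
| Hospital stay | primary (d), total time | primary, discharge date/time | absent | admission to discharge secondary in 4.4.2 |
| Cesarean rate | primary (e) | absent | absent | secondary in 4.4.2 |
| Admission to delivery | absent | absent | absent | power example in 5.1.1; named in 1.1; time of delivery secondary in 3.3.2 |

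Only the first row is consistent.

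**2. The plan's own power figures**

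Inputs from 5.1.1: n = 200 per group, d = 0.36 or 0.28 SD, SD 2 hours. Section 5.3 gives the 5% level but not the sidedness. Two-sided testing fits the stated figures. One-sided testing does not: it would give 97.5% and 87.6%.

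Normal approximation: power ≈ Φ(d√(n/2) − 1.96).
- d = 0.36: 0.36 × √100 = 3.60, so Φ(1.64) = 95.0% (noncentral t: 94.9%).
- d = 0.28: 0.28 × √100 = 2.80, so Φ(0.84) = 80.0% (noncentral t: 79.8%).
- In minutes: 0.36 × 120 = 43.2 and 0.28 × 120 = 33.6.

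The stated figures therefore reproduce, but only with 200 in each group.

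**3. The same calculation at 100 per arm (2.2)**

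- d = 0.36: 0.36 × √50 = 2.546, so Φ(0.586) = 72.1% (noncentral t: 71.7%).
- d = 0.28: 0.28 × √50 = 1.980, so Φ(0.020) = 50.8% (noncentral t: 50.4%).
- The difference detectable with 80% power rises to 0.398 SD. On the 2-hour SD of 5.1.1 that is 0.398 × 120 = 47.8 minutes.

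**4. False-positive chance with two primaries, if either could be presented as the primary result**

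Both nulls are taken as true, and each test holds its 5% level. For independent outcomes, the chance of at least one rejection is 1 − 0.95² = 9.75%. Counting only rejections in favour of outpatient care, it is 1 − 0.975² = 4.94%. The documents give no correlation, so the other rows assume one (bivariate normal).

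| Assumed correlation | Either direction | Favouring outpatient care |
|---|---|---|
| 0 | 9.8% | 4.9% |
| 0.6 | 8.8% | 4.4% |
| 0.9 | 7.0% | 3.5% |

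**5. What co-primaries would cost**

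Under Holm with two outcomes, an outcome is declared if its p ≤ 0.025, or if its p ≤ 0.05 and the other's p ≤ 0.025. By simulation (normal approximation) at 100 per arm and 0.36 SD, over correlations 0 to 0.9:
- other outcome null: about 62%;
- other outcome also 0.36 SD: about 66-68%.

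A single primary tested at 5% has 71.7%.

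**The case against.** The strongest defence is that 5.3 makes a deliberate choice. Each outcome is treated as its own question, all are named beforehand, FDR-adjusted values are reported alongside, and regression findings are set apart as exploratory. Unadjusted testing of separate questions is a respectable position, and the plan never says that one significant result makes the trial a success. This stands as far as it goes: the plan does not adopt an error-inflating success rule. But the position needs one fixed list, and the documents give three.

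Four stronger readings are tempting, and the documents do not support them.

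- **A large familywise error.** A reader might put the four superiority objectives of 3.1 into 1 − 0.95⁴ = 18.5%. That needs independence, all four nulls true and a rule that any one result counts. Hospital stay includes time to dilation, so those two are not independent. A null is also doubtful for time to dilation, because the admission clock starts at different points in the two arms.
- **Interim looks inflate the 5%.** Section 5.4 plans interim analyses every six months and gives no alpha rule. But 5.4 and 7.2.1 describe review and discontinuation driven by adverse outcomes or concern for harm, with no stopping for efficacy. That is a separate question, and inflation is not shown here.
- **Objective 3.1d is the same as the admission-to-discharge outcome of 4.4.2.** It speaks of total hospital time, which could include the outpatient placement visit before admission. The two are closely related but not clearly identical.
- **The 200 per group may be intended.** Section 5.1.1 also mentions a comparison group of all patients admitted for ripening and induction. The objectives, however, compare outpatient with inpatient ripening, and 2.2 gives those randomized arms 100 each.

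**Conclusion.** The point holds as a contradiction in the current text, not as missing detail. The three primary lists agree only on complete dilation. Section 4.4.2 demotes satisfaction, cesarean rate and admission-to-discharge time, although 3.1 or 3.3.1 has them (or, for 3.1d, the closely related total hospital time) as primary. Section 5.3 does not say which outcome decides.

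The error figure is modest and conditional: about 7-10% two-sided for two primaries, and 3.5-4.9% for false claims favouring outpatient care. It assumes that both nulls are true, that each test holds its level, that the correlation lies between 0 and 0.9, and that any one result could be presented as primary. The main harm is less the size of this number than that the rank of the reported primary result cannot be verified.

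The power consequence is firmer. On the randomized numbers in 2.2, power is about 72% at 0.36 SD and 50% at 0.28 SD, against the stated 95% and 80%.

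This should be corrected. It does not stop the trial or make its data unusable.

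**What to change.** Before any comparative data are seen:

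1. Make 3.1, 3.3.1, 3.3.2, 4.4.1, 4.4.2 and 4.4.4 agree on one primary outcome tested at 5%, or on named co-primaries with a stated alpha rule such as Holm. Label everything else secondary.
2. Add to 5.3 that the trial's conclusion rests on that primary and that all other outcomes are supportive, with FDR-adjusted values still reported.
3. State whether 3.1c means patient charges or system cost, and keep the two as separate outcomes.
4. If complete dilation is chosen, three gaps need closing:
   - The data list in 6.3 has delivery time but not complete dilation, so add it.
   - Admission comes after home ripening in the outpatient arm (4.2.1, item 8) but before Cervidil placement in the inpatient arm (4.2.2). State how the comparison will be interpreted.
   - Section 5.3 has no rule for women delivered by cesarean before full dilation, so add an analysis rule for them.
5. Restate 5.1.1 for the chosen primary at 100 per arm.

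The choice of primary is the sponsor's. Satisfaction or cost, which 2.2 puts first, are alternatives. Satisfaction would need one named score, and cost is not in the 6.3 list, although 4.4.1 names billing services as the source of patient charges.

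The cost is wording in several sections, possibly one added data item, and a less favourable stated power. A single primary loses no power relative to the present 5% test. Two co-primaries under Holm bring it to about 62-68% at 0.36 SD.
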